6.4 Description of Study Procedures/Evaluations

The primary deviation from standard education is described above in intervention implementation. The behavioral intervention is the use of the flexible curriculum tool to systematically tailor rotation resources to each learner. It will be utilized by one of the study personnel who are also the program director and associate program director of the fellowship program and primarily responsible for coordinating rotator education. The tool will output the recommended resources for each learner, which will then be passed along. A description of the tool, as well as a standard operating procedure for its utilization, is attached.

Self-Evaluations: All learners will be sent a self-evaluation describing their level of training and palliative care experience, preferred learning styles, time on the rotation and personalized learning goals.

Rotation Evaluation: Following the rotation, all learners have an opportunity to evaluate the rotation. Individuals not participating in the study can access a separate QR code/link in the body of the first survey email sent to them to provide rotation feedback in RedCap system. The QR code is in the Panda Palliative Care Office on the door and is available for all learners to provide anonymous feedback to faculty. The evaluations are provided at the end of the year to faculty. As standard of practice for the rotation, the program/rotation site director sends an email at the end of the rotation to the trainees with the same QR code as a reminder to complete these evaluations. This information can be found in document called

For those participating in the survey, a separate evaluation process will be utilized. Similar to standard of practice, evaluations will be sent via email and submitted through a different RedCap Survey. It is called “Post Rotation Evaluation.”

The focus group will be organized once all intervention group participants have submitted their evaluations by the end of January 2027. It will take place in February to early March 2027 over Microsoft Teams teleconferencing software and will use the attached focus group guide, developed using best practices.¹¹

As time rotating on the palliative care service can be emotionally distressing in general due to the nature of the work, trainees are offered frequent check-ins with faculty as well as psychosocial colleagues. They are also reminded of resources that they have through their training programs for mental health support, such as EAP, resident counseling, chaplain support, etc. Confidential information can be sent to palliative care administrators, trainee program directors, or CNH graduate medical education (GME) staff. Trainee performance or personal evaluations will not be impacted by their evaluations of the rotation. This will be the same for both control and intervention groups.

6.5 Study Team Training and Intervention Reliability

The intervention will be administered by the key personnel of the study. The flexible curriculum tool and database will not be updated during the intervention period, so all rotators during that period will have the same experience with the tool. It will be standardized, with standard operating procedures, which are attached, so it can be used by any user and yield the same recommendations for each learner based on the answers to their self-assessment.

6.6 Concomitant Interventions and Procedures

Participants are allowed to continue using any other educational tools while on the palliative care rotation. This does not limit their participation in the rotation or in the study.

Section 7: Safety Assessments and Reporting

Rotation with the palliative care team in general can be an emotionally difficult experience; however, there is no anticipated increased risk of adverse events during participation in the study, whether routine, severe, or unexpected and therefore would find no reason for the study to be halted.

Section 8: Statistical Considerations and Analysis

8.1 Statistical and Analytical Plans (SAP)

Because of the simple nature of this pilot study, there will not be a formal Statistical and Analytical Plan (SAP) apart from what is included in the IRB protocol.

8.2 Statistical Hypotheses

Primary Outcome Measure:

- Hypotheses:

- Null: There is no difference (in terms of central tendency) between the two groups in their response (using a Likert scale) to the question, “I achieved the standard objectives of the rotation.”
- Alternative: There IS a difference (in terms of central tendency) between the two groups in their response (using a Likert scale) to the question, “I achieved the standard objectives of the rotation.”

Secondary Outcome Measures:

- Hypotheses:
 - Null: There is no difference (in terms of central tendency) between the two groups in their response (using a Likert scale) to the question, “I achieved my specific objectives for the rotation.”
 - Alternative: There IS a difference (in terms of central tendency) between the two groups in their response (using a Likert scale) to the question, “I achieved my specific objectives for the rotation.”

For the remaining secondary outcome measures evaluated using a Likert Scale, the hypotheses will be like those of the above measures, as they are all evaluated using Likert scales.

For the secondary outcome measures evaluating using Likert Scales at pre- and post-participation time points, the hypothesis is as follows:

- Hypotheses:
 - Null: There is no difference in mean between the two groups in the degree of change between pre- and post-intervention confidence (for each individual objective)
 - Alternative: There IS a difference in mean between the two groups in the degree of change between pre- and post-intervention confidence (for each individual objective)

There are no hypotheses for the analysis of the open-ended survey questions and focus group data, as they will be analyzed using inductive thematic analysis.^{12,13}

8.3 Analysis Datasets

While the flexible education tool and database will be used for all participants in the intervention group to provide them with relevant resources, each individual learner is responsible for utilizing the resources themselves. Therefore, all participating subjects will be included in an intention-to-treat analysis dataset as opposed to per-protocol.

8.4 Description of Statistical Methods

This study is a pre-/post-interventional study; however, different participants will receive the intervention than those that receive the control education because of the nature of the palliative care rotation. Essentially, for the first 6 months of the study period, rotators will receive the control education, and for the next 6

months of the study period, they will receive education using the intervention, the flexible education tool. All evaluations from each 6-month period will be aggregated to preserve anonymity, and there will be no learners who are in both groups.

Demographic data will be collected during the self-assessment and reported using descriptive statistics:

- Level of training (categorically in percentages)
- Amount of experience in hospice and palliative medicine (categorically in percentage)
- Learning style (categorically in percentages)
- Time on palliative care service (categorically in percentages)

For all outcome measures that use Likert scales (ordinal data), the sample size is so small that it is assumed data will not fall within a normal distribution, so a Mann-Whitney U test will be to analyze it and report z-test statistic and p-value, as well as the interquartile range. A p-value of 0.05 will be used for statistical significance.

Individual participant data will not be published.

Confidence ratings will be compared at pre-post time points for significant improvements within each group using a paired t-test. Overall improvement between control and intervention groups will be compared using a student's t-test to compare the change in confidence. A p-value of 0.05 will be used for statistical significance.

Qualitative data, including responses to open-ended survey questions and focus group data, as mentioned in 8.2, will be analyzed using inductive thematic analysis using DeDoose software.

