3.4 Secondary Outcome Measure(s)

The secondary outcome measure is response to the question “I achieved my specific objectives for the rotation (which the learner provided at the start of the rotation).” It will be quantified using a Likert scale with five choices, 1-5, with 1 set to strongly disagree and 5 set to strongly agree.

Other outcome measures include whether (via Likert scale, scores ranging from Strongly Disagree to Strongly Agree as defined above):

- The learner was provided with a variety of resources to meet their learning objectives
- The education they received matched their level of training
- Their education was appropriate to their previous exposure to hospice and palliative medicine
- The education matched their learning style
- They felt the rotation was valuable

- The clinical educators promoted an open, respectful, and safe environment for discussion, learning, and improvement
- They would recommend this rotation to others

Open-ended feedback will be elicited regarding strengths of the rotation, areas for improvement, and practice changes, both on the survey and during the focus group.

Lastly, learners will be assessed on their confidence in meeting each standard rotation objective, on a Likert scale of 1-5, both before and after the rotation.

All of this allows the team to gather more information to understand why there was benefit for the flexible learning curriculum, if indeed there was one.

Section 4: Study Design

This is a single-center pilot study evaluating the use of a flexible curriculum tool to improve the experience of rotators with the palliative care team, measured by how well the rotation helps them meet standard as well as individualized learning objectives. It will not be blinded.

All learners will be sent a welcome email that will include a pre-rotation self-assessment, identifying type of learner and personal experience with palliative care, self-identified preferred ways of learning, length of time on the rotation, and personal learning goals.

All learners in the first half of the study period will be in the control group, and all learners in the second half of the study period will be in the intervention group. Outcomes will be measured on post-rotation evaluation surveys, one for each trainee, sent to them after their rotation is complete. Qualitative data will be more deeply interrogated with a focus group of trainees who participated in the intervention.

Section 5: Study Enrollment and Withdrawal

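### Do the t-tests on the confidence ratings break Section 8.4's own rule that Likert outcomes go to Mann-Whitney?

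*Protocol*

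**What the plan says.** Section 8.4 states a rule and a reason for it. The scope and the reason come first: "For all outcome measures that use Likert scales (ordinal data), the sample size is so small that it is assumed data". The second half of that sentence draws the conclusion: "will not fall within a normal distribution, so a Mann-Whitney U test will be to analyze it".

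The confidence ratings are Likert data by the protocol's own description. Section 3.4 says that "learners will be assessed on their confidence in meeting each standard rotation objective, on a Likert scale of 1-5, both before and after the rotation". Section 8.2 introduces their hypothesis with the words "For the secondary outcome measures evaluating using Likert Scales at pre- and post-participation time points".

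Section 8.4 nevertheless gives them a separate paragraph. Within groups: "Confidence ratings will be compared at pre-post time points for significant improvements within each group using a paired t-test". Between groups, it names a Student's "t-test to compare the change in confidence", and it repeats the 0.05 threshold. The null hypothesis in Section 8.2 fits those tests: "There is no difference in mean between the two groups in the degree of change between pre- and post-intervention confidence". The post-rotation Likert items, including the primary one, instead have hypotheses about central tendency.

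Section 8.1 adds that "there will not be a formal Statistical and Analytical Plan (SAP) apart from what is included in the IRB protocol".

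**The concern.** Taken literally, the general rule covers confidence, so the between-group comparison of confidence appears to have two tests: Mann-Whitney from the rule and Student's t from the dedicated paragraph. The stated reason for the rule (ordinal data and a sample too small to assume normality) applies equally to confidence, because the same learners supply those ratings, 10 to 15 per group under Section 8.5. The plan therefore seems to argue against a test that it then uses.

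If the choice really were open, two p-values would be available for each standard objective and one could be preferred after the data are seen. Because Section 8.1 rules out a separate SAP, no later document would settle it. A t-test that misbehaved on short, capped scales at this sample size would make matters worse, since some confidence findings could then be spurious.

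**Working it through.** **Step 1: which test is planned?**

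| Outcome | Hypothesis (8.2) | Test (8.4) |
|---|---|---|
| Likert items rated after the rotation, including the primary | central tendency, between groups | Mann-Whitney |
| Confidence, between groups | mean of the change | Student's t-test on change |
| Confidence, within group | none stated separately | paired t-test |

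Hypothesis and test agree in both between-group rows. Mann-Whitney compares independent groups, so it could not serve for the within-group row; there only the normality rationale conflicts. Read with the specific text governing the general, each comparison has one test.

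**Step 2: is that test sound at this size?** The protocol gives no power or variance figure to reproduce, so this was checked by simulation.

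Inputs from the protocol: 1-5 scale (3.4), n = 10 or 15 per group (8.5), threshold 0.05 (8.4), non-directional hypotheses (8.2). Assumed inputs: pre-rotation mean 3 in both groups, control post-rotation mean 3.7, 4.0 or 4.3, SD 0.7, 0.9 or 1.1, pre/post correlation 0.3 or 0.6, tool effect 0, 0.5 or 1 point, normal scores rounded and capped at 1-5. That is 3 × 3 × 2 × 2 × 3 = 108 settings, with 2,000 runs each.

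For each learner, change D = post − pre. The t-test uses t = (mean D in intervention − mean D in control) / [s_p √(1/n₁ + 1/n₂)], where s_p is the pooled SD of D, on n₁ + n₂ − 2 degrees of freedom (18 or 28). Mann-Whitney ranks the same D values and uses the normal approximation.

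Results over the grid:
- Rejection with no effect: t-test 4.3-5.8%, Mann-Whitney 3.9-5.5%. Simulation error at 2,000 runs is √(0.05 × 0.95 / 2000) = 0.49 points, so 5% ± 1.96 × 0.49 is about 4.0-6.0%. The whole t-test range lies inside that band.
- Different verdicts from the two tests: 0.9-2.1% of runs with no effect, 2.0-5.0% with 0.5 point, 2.7-5.7% with 1 point.
- Within the control group, paired t-test and Wilcoxon signed-rank differ in 0-3.6% of runs.

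Central case (SD 0.9, correlation 0.3, control post-rotation mean 4; 20,000 runs):

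| n per group | Effect | t-test | Mann-Whitney | Verdicts differ | t-test only | Mann-Whitney only |
|---|---|---|---|---|---|---|
| 10 | 0 | 4.9% | 4.3% | 1.4% | 1.0% | 0.4% |
| 10 | 0.5 | 12.8% | 11.2% | 2.8% | 2.2% | 0.6% |
| 10 | 1 | 30.5% | 27.8% | 4.5% | 3.6% | 0.9% |
| 15 | 0 | 4.9% | 4.7% | 1.4% | 0.8% | 0.5% |
| 15 | 0.5 | 17.3% | 16.2% | 3.3% | 2.2% | 1.1% |
| 15 | 1 | 43.9% | 41.0% | 5.5% | 4.2% | 1.3% |

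The power differences are 12.8 − 11.2 = 1.6, 30.5 − 27.8 = 2.7, 17.3 − 16.2 = 1.1 and 43.9 − 41.0 = 2.9 points. Part of each gap arises because Mann-Whitney runs slightly below 5% with no effect. With groups of 10 and 15 the differences are 15.3 − 13.5 = 1.8 and 37.6 − 34.1 = 3.5 points, and the t-test's rate with no effect is 5.0%.

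**Step 3: does a different rating model agree?** With latent correlation 0.5 and other baselines and gains, the rates with no effect were 4.8-5.2% (t-test) and 4.2-4.5% (Mann-Whitney). Verdicts differed in about 1-6% of runs. Power for a latent difference of 1.0 was 44% against 40% at n = 10 and 61% against 58% at n = 15. Within group, with no true change, the paired t-test rejected in 4.6-5.3% of runs and signed-rank in 4.1-4.6%.

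**The case for a change.** The case for a change is that this protocol is the whole analysis plan, that its only stated reason for choosing a test covers confidence as well, and that a reader cannot tell a reasoned exception from an oversight. Consistency would then point to Wilcoxon signed-rank within group and Mann-Whitney on change between groups, with the Section 8.2 hypothesis reworded to match.

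Part of this stands. The word 'all' reaches too far, and no reason is given for treating confidence differently. The rest does not carry a change. The dedicated paragraph and the mean-change hypothesis fix the planned test before any data are compiled, so the room for choosing afterwards is slight. Rank tests would answer only half of the plan's reason: signed-rank, and Mann-Whitney on change, also start by subtracting one 1-5 rating from another, so they treat the steps as equal just as the t-test does. They would also give up a little power in a pilot that Section 8.5 already accepts may be underpowered. Statisticians differ on that trade-off, and the plan's choice is defensible.

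Any analysis of change needs each learner's two ratings joined. Section 6.1 says responses are not tied to identity, while Section 10.4 assigns a study number that could join them without identity. This need is the same for t-tests and rank tests, so it does not bear on the choice between them.

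**Conclusion.** The inconsistency is real but clerical. The specific text in Sections 8.2 and 8.4 settles the analysis of confidence as t-tests on change, and an analyst who follows it obtains valid results. Rejection with no effect stays at 4.3-5.8%, the verdict would differ from a rank test's in roughly 1-6% of runs, and replacing the t-tests would cost about 1 to 4 points of power. Narrowing the Mann-Whitney sentence to the items rated only after the rotation would tidy the text and alter no result. The primary outcome is a single post-rotation item under Mann-Whitney and is unaffected.

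These sizes rest on assumed means, SDs, correlations and a rounded, capped normal model, because the protocol gives no rating data. Two different sets of assumptions gave the same picture. No change to the plan is called for.

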5.6 Retention

- All study subjects in the control group will only participate in the study for the extent of one survey
- Study subjects in the intervention group will participate in the study for the extent of one survey

- Subjects in the intervention group will then be recruited to possibly participate in a single focus group
- Participants will be incentivized to participate in the focus group with a \$20 gift card to a location approved by the IRB to compensate them for their time

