5.7 End of Participation Criteria and Procedures

Participants are free to withdraw from participation in the study at any time upon request. Their participation in the study is only when they complete their evaluation form and if they choose to participate in the focus group. For those that require evaluations for their training programs, study participation does not affect their ability to participate successfully in a rotation with the palliative care team or receive positive evaluations, since the processes are independent.

Participants may also withdraw during the focus group.

Section 6: Study Procedures

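### The paired and change-score confidence tests need each learner's two ratings joined, but the protocol describes one post-rotation survey and never says how the join is made

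*Protocol*

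**What the plan says.** On the analysis side:

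- Section 3.4 has learners rate their "confidence in meeting each standard rotation objective, on a Likert scale of 1-5, both before and after the rotation".
- Section 8.2 sets a hypothesis, objective by objective, about the between-group difference in mean change, for measures "evaluating using Likert Scales at pre- and post-participation time points".
- Section 8.4 fixes the tests: "Confidence ratings will be compared at pre-post time points for significant improvements within each group using a paired t-test", and between groups a Student's "t-test to compare the change in confidence". It also pools the evaluations from each six-month period to protect anonymity.

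On the conduct side:

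- Section 5.6: "All study subjects in the control group will only participate in the study for the extent of one survey". For the other group: "Study subjects in the intervention group will participate in the study for the extent of one survey", followed by a possible focus group.
- Section 5.7: "Their participation in the study is only when they complete their evaluation form and if they choose to participate in the focus group".
- Sections 6.1 and 6.2 take consent after the rotation, at the evaluation form, and 6.1 promises that identity is not linked to responses.
- Section 10.4 says research data will carry a unique study number for each participant.
- Sections 8.6 and 11.1 remove identifying information when the data are compiled, in August 2026 for control and February 2027 for intervention.

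A pre-rotation self-assessment does exist. Section 4 and section 6.4 send it to all learners, and 6.3 describes its content.

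**The concern.** A paired t-test and a t-test on individual change both work on within-learner differences. If the pre-rotation form and the Post Rotation Evaluation cannot be joined learner by learner, those differences do not exist and neither test can be run as written. Careful analysis cannot repair this afterwards, because pairs collected without a common key cannot be reconstructed. Section 8.1 also says that no formal analysis plan is intended beyond this protocol, so the protocol itself has to settle the point.

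At stake is the set of confidence hypotheses in 8.2. The primary outcome, the learner-specific objective and the other Likert items asked only after the rotation need no matching.

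**Working it through.** **What the tests require.** The protocol gives no effect size, SD or power for the confidence ratings, so there is no stated figure to reproduce. For one objective in one group of n learners, with differences d = post − pre:

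- paired statistic: t = mean(d) / (s_d / √n)
- s_d² = s_pre² + s_post² − 2·ρ·s_pre·s_post, where ρ is the pre-post correlation within learners.

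Unmatched data give both means and both SDs, and so the mean change. They do not give ρ, and so not s_d. The between-group test has the same gap: the difference in mean change can be estimated from four group means, but its change-score variance cannot.

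**Number of tests affected.** Per standard objective: 2 within-group paired tests + 1 between-group test = 3. The number of standard objectives is not stated.

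**Is a join described?** Four steps would be needed.

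1. *A pre-rotation rating collected on a named form.* Section 4, 6.3 and 6.4 each list the content of the self-assessment, and none names a confidence rating. The nearest entry is the mention of standard objectives in 6.3. For the control period, 6.3 describes an introductory email and objectives shared on the first day. It describes answering the self-assessment only for July to December learners, although Section 4 and 6.4 send the form to everyone.
2. *A common key on both forms.* The study number in 10.4 is a candidate. No section says when it is assigned or which forms carry it.
3. *Matching before identifiers are removed.* Sections 8.6 and 11.1 leave time for this but do not mention it.
4. *Agreement that covers the earlier answers.* Section 5.7 confines participation to the evaluation form and focus group. Yet 8.4 already uses the earlier form as study data: "Demographic data will be collected during the self-assessment and reported using descriptive statistics".

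None of the four steps is stated clearly.

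**What losing the match costs (illustration).** Assume equal pre and post SDs and ρ of 0.3, 0.5 or 0.7; none of these values is in the protocol. If the within-group comparison treats the two sets of ratings as independent, its standard error relative to the paired one is √2 / √(2(1−ρ)) = 1/√(1−ρ):

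| ρ (assumed) | SE ratio, unmatched to paired |
|---|---|
| 0.3 | 1/√0.7 = 1.20 |
| 0.5 | 1/√0.5 = 1.41 |
| 0.7 | 1/√0.3 = 1.83 |

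**What the simplest fallback costs.** Comparing post-rotation confidence between groups needs no matching. Its standard error relative to the change-score comparison is 1/√(2(1−ρ)): 1/√1.4 = 0.85, 1/√1.0 = 1.00 and 1/√0.6 = 1.29 for the same three correlations. Precision is therefore not necessarily worse. What is lost is the allowance for baseline differences between two non-randomised, consecutive groups.

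**The case against.** The strongest reply is that the protocol leaves the mechanism under-described but does not exclude it. Section 6.1 bars a link from identity to response, which is not the same as barring a code shared by two forms. Section 10.4 supplies a participant number. Identifying information is removed only at compilation, so record-level information exists until then. In the intervention period the self-assessment must be attributable to a learner, because a curriculum is built from it. The one-survey wording in 5.6 may count only what a person completes as a consented participant, and the standard objectives mentioned in 6.3 may be the confidence items in summary. The forms are not shown. The pooling in 8.4 may mean only that records are grouped by period.

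All of that stands, and it rules out saying that matching is forbidden or that the confidence items are absent. It does not supply the missing steps: no section assigns the number before the rotation, places it on both forms or describes a match. Nor is the join a formality. Section 6.4 has the tool operated by the program director or associate program director, so joining an attributable self-assessment to the evaluation would tie a known trainee to ratings of the rotation those directors coordinate. Section 6.1 promises otherwise.

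A reader might also infer two stronger points that the documents do not support:

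- *That control pairs have already been lost*, because version 6 (02/11/2026) falls inside the January to June 2026 control period. The date says nothing about whether forms already carry a code, and versions 5 and 6 are logged only as wording edits.
- *That the learner-characteristics table will include people who did not join the study*, because the self-assessment goes to everyone. Section 8.3 limits the analysis dataset to participating subjects, and any estimate of contamination would rest on assumed return rates.

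**Conclusion.** The point holds as an inconsistency that should be reconciled. Sections 3.4, 8.2 and 8.4 require matched ratings. Sections 5.6, 5.7 and 6.1 describe one unlinked post-rotation survey, and 10.4 offers a possible key that is never put to use. The consequence is conditional: if the one-survey, unlinked wording is followed, all three confidence tests for each standard objective cannot be computed as specified. If the 10.4 number is in fact on both forms, the tests are feasible and only the text is at fault. A retrospective rating of earlier confidence on the post-rotation survey would also remove the need for a link, but 3.4 and 8.2 read as two separate occasions and no section describes such an item.

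The standard-error ratios rest on assumed correlations. They show the scale of the loss and are not evidence of the defect. The effect is confined to the confidence hypotheses, in a pilot that accepts in 8.5 that it may be underpowered.

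**What to change.** - Put one code on both the pre-rotation self-assessment and the Post Rotation Evaluation, in both groups. It can be the 10.4 study number, with the key held only by the study coordinator and removed at export, or a code that the learner generates.
- State that the confidence items are on both forms.
- Have the information sheet cover use of the pre-rotation answers, since consent comes later.
- Make 5.6, 5.7, 6.1, 8.4 and 10.4 agree on the number of forms, the code and the matching step.
- Where linkage is not possible, replace the paired and change-score tests with a comparison that needs no matching, such as post-rotation confidence between groups, or report confidence descriptively by time point.
- If a retrospective rating was meant, say so in 3.4, 8.2 and 8.4.

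The cost is an IRB amendment and a small REDCap edit. Some codes will fail to match. At an assumed failure rate of 10% to 30%, 10 participants leave 10 × 0.7 to 10 × 0.9 = 7 to 9 pairs, and 15 leave 15 × 0.7 to 15 × 0.9 = 10.5 to 13.5, or about 10 to 13 pairs per group.

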8.5 Sample Size

Because this is a pilot study to improve the education of an existing population on a rotation with a small team, the sample will be a convenience sample of learners who rotate with the palliative care team. It is expected that there will be approximately 20 learners to recruit and screen for each (control and intervention) group and to enroll at least 10 and up to 15 for each group. It is accepted that the statistical analysis may be underpowered, which is why the pilot study will be supplemented with qualitative data.

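### Student's t-test for the between-group change in confidence does not hold its 5% level if group sizes and spreads both differ; name Welch's test, and give 8.2 and 8.4 the same unit of analysis

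*Protocol*

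**What the plan says.** Section 3.4 states that "learners will be assessed on their confidence in meeting each standard rotation objective, on a Likert scale of 1-5", before and after the rotation. The number of standard objectives is not given.

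Section 8.2 sets a null hypothesis for this outcome: "There is no difference in mean between the two groups in the degree of change between pre- and post-intervention confidence (for each individual objective". The alternative is two-sided and also framed per objective.

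Section 8.4 gives the method: "Overall improvement between control and intervention groups will be compared", by a Student's "t-test to compare the change in confidence". It adds: "A p-value of 0.05 will be used for statistical significance". It names no unequal-variance form and defines no mean, sum or other overall score.

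Section 8.5 expects to "enroll at least 10 and up to 15 for each group". Section 8.6 says there is no randomisation, and group membership follows the calendar half in which the learner rotates. Section 8.1 says there will be no formal analysis plan beyond the protocol, so what 8.2 and 8.4 say is the plan.

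**The concern.** Student's test estimates one common variance. That does little harm when the groups are the same size. When sizes differ, the pooled estimate leans towards the larger group, and the standard error is too small or too large according to which group is the more variable.

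This design prevents neither condition. Sizes depend on who rotates and who consents. Learners range from shadowing students to fellows, and section 2.2 puts time on service between half a day and a few months. The mix may differ between the two halves, and with it the spread of change.

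The second matter is what is tested. Section 8.2 implies one test per objective. Section 8.4 can be read as one test on an overall score. The number of tests at 0.05, and what a significant result would mean, depend on which is intended.

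**Working it through.** **Inputs from the protocol.** 10 to 15 learners per group (8.5); Student's t-test at 0.05 (8.4); two-sided hypothesis on mean change (8.2). The protocol gives no SD, effect size, power or number of objectives for this outcome, so it has no figure to reproduce.

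**Assumptions.** SD ratio between groups of 1, 1.5 or 2; normal change scores, with a check on integer scores; 10 versus 15 as the most unequal split in the stated range.

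**Step 1: why the level moves.** The true variance of the difference in means is s1²/n1 + s2²/n2. Student's test targets sp² × (1/n1 + 1/n2), where sp² = [(n1−1)s1² + (n2−1)s2²] / (n1+n2−2).

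- Smaller group more variable (n1 = 10, s1 = 2; n2 = 15, s2 = 1). True: 4/10 + 1/15 = 0.467. Pooled: (9×4 + 14×1)/23 × (1/10 + 1/15) = 2.174 × 0.1667 = 0.362. The standard error is √(0.362/0.467) = 0.88 of what it should be, so the test rejects too often.
- Larger group more variable (s1 = 1, s2 = 2). True: 1/10 + 4/15 = 0.367. Pooled: (9×1 + 14×4)/23 × 0.1667 = 0.471. The standard error is √(0.471/0.367) = 1.13 times what it should be, so the test rejects too rarely.
- Equal sizes: the two expressions are identical whatever the SDs.

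**Step 2: simulated rejection of a true null** (200,000 trials per setting, two-sided 0.05).

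| Setting | Student | Welch |
|---|---|---|
| 10 v 15, equal SD | 5.0% | 5.0% |
| 10 v 15, smaller group SD × 1.5 | 7.0% | 5.0% |
| 10 v 15, smaller group SD × 2 | 8.6–8.7% | 5.0–5.2% |
| 10 v 15, larger group SD × 1.5 | 3.5–3.6% | 4.9% |
| 10 v 15, larger group SD × 2 | 3.0–3.1% | 4.9% |
| 10 v 10 or 15 v 15, SD ratio 2 | 5.3–5.5% | 4.9–5.1% |

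Ranges cover repeat runs of equivalent settings. Integer change scores at 10 v 15 and a 2:1 ratio agree: Student 8.7% or 2.9%, Welch 5.0% or 4.8%.

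**Step 3: cost of Welch if variances are equal.** Power for a 1 SD difference is 65.0% (Student) versus 63.9% (Welch) at 10 v 15, 56.1% versus 55.5% at 10 v 10, and 75.3% versus 75.1% at 15 v 15.

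**Step 4: why the unit matters.** One test keeps 5%. With k independent tests at 0.05, the chance of at least one false positive is 1 − 0.95^k: 14.3% for k = 3, 22.6% for 5, 33.7% for 8 and 40.1% for 10. With correlations of 0.3 to 0.7 between objectives and k = 3 to 10 it is about 11% to 36%. Both k and the correlation are assumptions.

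**Step 5: is a mean over objectives better?** Its SD relative to one objective is √[(1 + (k−1)ρ)/k]. For k = 5 and ρ = 0.5 this is √(3/5) = 0.775. At 15 per group, a 0.6 SD shift (assumed) on one objective has about 35% power. If all five objectives shift by 0.6 SD, the standardised shift in the mean is 0.6/0.775 = 0.77 and power is about 54%. If only two of five shift, it is (0.6 × 2/5)/0.775 = 0.31 and power is about 13%. The gain depends on the objectives moving together.

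**The case against.** On the test, the plan aims for balance: the protocol summary anticipates 15 per group, and about 20 are to be screened for each. At equal sizes Student's test is close to nominal. The protocol offers no evidence that spreads will differ, and variation in time on service exists within both halves. This stands, and it makes the point conditional. A reader might infer from the 8.6–8.7% figure that the false-positive rate is nearly double. The documents do not support that: it requires the most unequal split in the range and twice the SD in the smaller group, and the mirror case gives about 3%. Nor does Welch's test add precision.

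On the unit, a reader might infer that 8.2 and 8.4 plainly contradict each other. The sentence before the one quoted from 8.4 concerns improvement within each group, so the word overall may simply introduce the between-group contrast, with 8.2 supplying the unit. That reading is fair, so this is an ambiguity and not a proven contradiction. It still needs settling, because 8.4 does not repeat the unit and no later plan is foreseen.

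A reader might also conclude that a mean score should replace the per-objective tests. Step 5 shows a trade-off. The intervention tailors resources to each learner, so a uniform shift cannot be presumed, and a mean score would answer a different question from the one 8.2 sets.

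The argument that the form of the t-test can be left to the statistical consultant carries less weight, because 8.1 makes this text the whole plan.

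**Conclusion.** The point holds as a conditional weakness, and it is minor. If sizes and spreads both differ, Student's test can run at about 7% to a little over 8.5%, or at about 3% to 3.6%, instead of 5%. If either is equal, the error is nil or small (at most 5.5%). These figures rest on assumed SD ratios of 1.5 to 2 and a 10 versus 15 split. The wording of 8.2 and 8.4 leaves the unit of analysis open and should be reconciled; the documents do not show which reading is meant.

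The outcome is secondary, in a pilot whose section 8.5 already accepts that the analysis may be underpowered. The primary outcome is not affected.

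The point also assumes that change can be computed for each learner. Section 5.6 limits participation to one survey (plus the focus group), and section 6.1 says nothing will link identity to responses, while 10.4 mentions a unique study number. If ratings before and after cannot be paired, neither form of the test on change can be run.

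**What to change.** In section 8.4, name Welch's t-test for the between-group comparison of change in confidence. It needs no new data and costs about 1 point of power at most if the variances are equal.

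In sections 8.2 and 8.4, state the same unit, by one of two routes:

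- Keep the per-objective hypotheses of 8.2, and say in 8.4 that the comparison is made for each objective. This keeps the question as set, with several tests at 0.05 to be read accordingly.
- Define one score, such as each learner's mean change over all standard objectives, with a single comparison and the individual objectives described only. This gives one test, and more precision if the objectives shift similarly. It gives up formal tests of single objectives and loses power if only a few of them shift.

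Either route is a sentence or two of editing, best done before any outcome data are analysed.
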